5.4. Secondary Endpoints Analyses

The secondary efficacy endpoint analysis will be performed on the FAS. Analyses for change from Baseline to Week 8 in the QMG total score, MG-ADL total score, and Neuro-QoL Fatigue score will be performed using both the FAS and PPS. Unless otherwise specified, baseline is defined as the last available assessment prior to the first dose of study intervention. The analysis results will be reported by treatment group for the PEP. For QMG, in the event that cholinesterase inhibitor was not withheld for at least 8 hours prior to administration of the QMG test on Day 1, the Screening Visit assessment will be used as Baseline. If cholinesterase inhibitor was not withheld for these visits (both Day 1 and Screening Visits), the Day 1 assessment will be used as baseline.

All secondary endpoint analyses will be performed at the first analysis (Week 8).

5.4.1. Secondary Endpoints

5.4.1.1. Change From Baseline in the QMG Total Score at Week 8

The analysis will be performed on the FAS and PPS population.

A mixed-effects model with repeated measures (MMRM) will be used to estimate the treatment effect using all available data up to Week 8, irrespective of whether participants received rescue therapy. Missing data will not be imputed for the analysis.

The MMRM will include change from Baseline at each prespecified timepoint (Weeks 1, 2, 3, 4, 5, 6, 7, and 8) as the response variable; treatment group, study visit, and treatment-by-study visit

interaction as fixed categorical effects; and the baseline QMG total score as a covariate. The treatment effect will be evaluated via contrast for the treatment-by-visit term at Week 8. An unstructured covariance matrix will be used to model the correlations among repeated measurements within each participant. If a convergence issue occurs or the model performs poorly, alternative covariance matrix structures will be used in the following order until convergence or model performance issue is resolved: Toeplitz (TOEP), first order autoregressive (AR(1)), Compound symmetry (CS).

The Kenward-Rogers method will be used to estimate the denominator degrees of freedom.

The following statistics will be presented:

- Least-squares (LS) means per treatment group
- Standard error of LS means
- 90% CI
- LS mean difference (180 mg , 120 mg versus placebo, 180 mg versus 120 mg bid) and 90% CI of OR
- P-value for testing differences between treatment groups

Absolute levels and the change from Baseline in the QMG total score will be summarized in descriptive statistics by study visits and treatment groups.

A trend analysis to detect whether there is a decreasing (dose response) trend in the change from Baseline at Week 8 in the QMG total score will be presented, along with the p-value using the Jonckheere-Terpstra trend test.

5.4.1.2. Change From Baseline in the Neuro-QoL Fatigue Total Score at Week 8

The analysis method and missing data handling will be the same as described in Section 5.4.1.1. (with the baseline Neuro-QoL Fatigue total score as a covariate and change from Baseline to Week 4 and Week 8 as the response variable in the MMRM model)

5.4.1.3. Change From Baseline in the MG-ADL Total Score at Week 8

The analysis method and missing data handling will be the same as described in Section 5.4.1.1 (with the baseline MG-ADL total score as a covariate and change from Baseline at each prespecified timepoint as the response variable in the MMRM model).

5.4.1.4. Proportion of Participants With at Least a 3-, 4-, 5-, 6-, 7-, or 8-Point Improvement in the QMG Total Score at Week 8

The analysis will be performed on the FAS.

The proportions of participants with the various point improvement in QMG in each treatment group and study visit will be presented, along with exact 2-sided 90% CIs using the Clopper-Pearson method. The differences in proportions between each of the ALXN2050 dose groups (180 mg bid or 120 mg bid) and the placebo group will be presented, along with 2-sided 90% CIs using the Chan and Zhang method (Chan, 1999). No imputation will be implemented.

5.4.1.5. Proportion of Participants With at Least a 2-, 3-, 4-, 5-, 6-, 7-, or 8-Point Improvement in the MG-ADL Total Score at Week 8

The analysis method and missing data handling will be the same as described in Section 5.4.1.4.

5.4.1.6. Proportion of Participants With at Least a 3-, 4-, 5-, 6-, 7-, or 8-Point Improvement in the QMG Total Score in Any 4 Consecutive Weeks During the First 8 Weeks and Who Did Not Receive Rescue Therapy

The analysis will be performed on the FAS.

The proportions of participants with the various point improvement in QMG in any 4 consecutive weeks during the first 8 weeks and who did not use rescue therapy will be presented by treatment group and study visit, along with exact 2-sided 90% CIs using the Clopper-Pearson method. The differences in proportions between each of the ALXN2050 dose groups (180 mg bid or 120 mg bid) and the placebo group will be presented, along with 2-sided 90% CIs using the Chan and Zhang method (Chan, 1999).

Participants who discontinued early without achieving the above specified response will be considered as nonresponders. Participants who received rescue therapy anytime during the first 8 weeks will be considered as nonresponders.

5.4.1.7. Proportion of Participants With at Least a 3-, 4-, 5-, 6-, 7-, or 8-Point Improvement in the MG-ADL Total Score in Any 4 Consecutive Weeks During the First 8 Weeks and Who Did Not Receive Rescue Therapy

The analysis method and missing data handling will be the same as described in Section 5.4.1.6.

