## 9.4.6.2. Analyses of Secondary Efficacy Endpoints

For all continuous secondary endpoints (QMG total score, MG-ADL total score, Neuro-QoL™ Fatigue score) related to the change from baseline at Week 8, the mixed-effects model with repeated measures (MMRM) will be used to estimate the treatment effect using all available data, irrespective of whether participants received rescue therapy. Missing data will not be imputed for the analysis. For each of the continuous secondary endpoints, the MMRM will include change from baseline at each prespecified time point as the response variable, treatment group, study visit, and treatment-by-study visit interaction as fixed categorical effects, and baseline total score as a covariate. The treatment effect will be evaluated via contrast for the treatment-by-visit term at Week 8. An unstructured covariance matrix will be used to model the correlations among repeated measurements within each participant. Other covariance structures will be implemented if a convergence issue occurs (details to be provided in the SAP). The Kenward-Rogers method will be used to estimate the denominator degrees of freedom.

Trend analysis to detect whether there is a decreasing trend in the change from baseline at Week 8 in MG-ADL total score will be presented along with the p-value using Jonckheere-Terpstra trend test.

For the categorical secondary endpoints:

• Proportion of participants with at least a 3-, 4-, 5-, 6-, 7-, or 8-point improvement in the QMG score at Week 8

- Proportion of participants with a QMG score reduction of  $\geq$  3 points in any 4 consecutive weeks during the first 8 weeks and who did not receive rescue therapy
- Proportion of participants with at least a 2-, 3-, 4-, 5-, 6-, 7-, or 8-point improvement in the MG-ADL total score at Week 8
- Proportion of participants with at least a 3-, 4-, 5-, 6-, 7-, or 8-point improvement in the MG-ADL total score in any 4 consecutive weeks during the first 8 weeks and who did not receive rescue therapy
- Proportion of participants with at least a 4-, 5-, 6-, 7-, or 8-point improvement in the QMG total score in any 4 consecutive weeks during the first 8 weeks and who did not receive rescue therapy

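### If the unstructured MMRM is abandoned, every SAP fallback assumes equal variance at all visits, so the Week 8 standard error can be wrong in either direction, and part of the trigger is undefined

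*SAP*

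**What the plan says.** SAP 5.4.1.1 sets out the model for change from baseline in QMG. The response is the change at each of eight visits, "Weeks 1, 2, 3, 4, 5, 6, 7, and 8) as the response variable". The first-choice covariance is unstructured: "An unstructured covariance matrix will be used to model the correlations among repeated measurements within each participant". The tested quantity is one visit: "The treatment effect will be evaluated via contrast for the treatment-by-visit term at Week 8".

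The fallback begins "If a convergence issue occurs or the model performs poorly", and the structures are then tried in a fixed order: "Toeplitz (TOEP), first order autoregressive (AR(1)), Compound symmetry (CS"). The sequence stops once the convergence or performance problem is resolved. No criterion for performance is given. Kenward-Roger is named for the degrees of freedom, and no robust standard error is specified.

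SAP 5.4.1.3 applies the same method to MG-ADL. SAP 5.4.1.2 applies it to Neuro-QoL Fatigue with only two visits: "change from Baseline to Week 4 and Week 8 as the response variable in the MMRM model".

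Protocol 9.4.6.2 names one trigger: "Other covariance structures will be implemented if a convergence issue occurs (details to be provided in the SAP"). SAP Appendix 4 declares no change from the protocol-planned analyses. Among the secondary efficacy analyses, the SAP addendum for the final analysis keeps only the QMG and MG-ADL change-from-baseline analyses.

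**The concern.** In SAS, TOEP, AR(1) and CS are equal-variance structures. They differ in how they model correlation between visits, but each estimates one variance for all visits. The heterogeneous versions have their own names (TOEPH, ARH(1), CSH) and are not listed. Once the unstructured matrix is left, the Week 8 standard error is driven by something close to the average variance over Weeks 1 to 8 instead of the variance at Week 8. Kenward-Roger adjusts for small samples given the chosen covariance model; it does not correct a wrong one.

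The second issue is the trigger. The protocol lets the analyst leave the unstructured matrix only for non-convergence. The SAP adds a condition with no definition, so two analysts could reasonably disagree on whether it is met, and on whether to stop at the next structure or go on.

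At stake are the p-values and 90% CIs for the two Week 8 contrasts that the addendum retains.

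**Working it through.** **Inputs from the documents.** Eight visits; contrast at Week 8; two-sided type I error 10% (SAP 5.1); about 70 participants randomised 2:1:2 (SAP 1.2), taken here as 28:14:28. The documents give no SD, correlation or standard error for the MMRM, so the plan has no figure of its own to reproduce.

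**Assumptions.** SD paths as in the table; between-visit correlation either constant at 0.7 or autoregressive at 0.85; complete data; baseline covariate ignored.

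**1. Size of the models.** Unstructured: 8 × 9 / 2 = 36 parameters. TOEP: 8. AR(1) and CS: 2 each. A heterogeneous form replaces one variance by eight, so it adds 7: TOEPH 15, ARH(1) and CSH 9 each.

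**2. Formula.** With complete data and a full treatment-by-visit mean, the estimated Week 8 difference is the simple difference in Week 8 means under any of these covariances. Only the standard error changes:

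model SE / correct SE = fitted common SD / true Week 8 SD = r

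true two-sided error = 2 × (1 − Φ(1.645 × r))

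The fitted SD is the Gaussian-likelihood limit for each structure. For CS it is the square root of the mean visit variance.

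**3. One case in full (CS, SD rising linearly from 2.2 to 3.2).** Visit SDs are 2.20, 2.34, 2.49, 2.63, 2.77, 2.91, 3.06 and 3.20. Mean variance 7.397; fitted SD 2.720. r = 2.720 / 3.2 = 0.850. 1.645 × 0.850 = 1.398. Error = 2 × (1 − Φ(1.398)) = 16.2%, so a 90% CI covers about 84%.

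**4. All paths (range over TOEP, AR(1), CS and both correlations).**

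| SD of change, Week 1 to Week 8 | r | True error (nominal 10%) |
|---|---|---|
| 2.5 to 3.0, linear | 0.92 | 13.1% |
| 2.2 to 3.2, linear | 0.85 | 16.0-16.2% |
| 1.8 to 3.5, linear | 0.77-0.78 | 19.8-20.3% |
| 2.5 to 3.0 by Week 3, then flat | 0.95-0.97 | 11.0-11.7% |
| 2.2 to 3.2 by Week 3, then flat | 0.92-0.95 | 11.9-13.2% |
| 1.8 to 3.5 by Week 3, then flat | 0.88-0.92 | 12.8-14.7% |
| constant | 1.00 | 10.0% |
| 3.0 to 2.5, linear | 1.10 | 7.0% |
| 3.2 to 2.2, linear | 1.24 | 4.1-4.2% |

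On the linear paths the three structures agree to within about half a point. On the plateau paths they differ by up to 2 points.

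**5. Simulation check.** 28:14:28, 40,000 runs per case, autoregressive correlation 0.8, with the mean visit variance standing in for an equal-variance fit. For a Week 8 to Week 1 SD ratio of 1.0, 1.25, 1.5 and 2.0, the equal-variance error was 9.5%, 13.3%, 16.2% and 20.4%. With the Week 8 variance itself, as under unstructured, it was 9.7-10.1% throughout.

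**6. Heterogeneous forms.** For SD ratios 1.25 to 2.0, with true correlation constant at 0.6 or autoregressive at 0.8, fitted Week 8 SD / true Week 8 SD is 1.00 for TOEPH and ARH(1). For CSH it is 1.00 or 1.06, the latter when the true correlation is autoregressive. None understates the Week 8 standard error.

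**7. Neuro-QoL.** With two visits, TOEP, AR(1) and CS are the same two-parameter model, and the unstructured matrix has only three parameters. Failure of that fit is unlikely, so the point concerns QMG and MG-ADL.

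**The case against.** The specified model is unstructured. Eight weekly clinic visits in about 70 participants give up to 560 observations for 36 covariance parameters, planned non-evaluability is about 5%, and nothing in the documents suggests the fit will fail. This stands: the problem is conditional, and its probability cannot be stated from the documents.

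A reader might infer that the retained p-values and CIs are anti-conservative. The documents do not support that. They contain no SDs, and a falling SD makes the test conservative. There are reasons to expect some growth: Week 1 change is close to baseline, response status diverges later, and data after rescue are kept. But the protocol also expects rapid onset, which fits an early plateau at least as well as steady growth and roughly halves the excess. Rapid onset describes means, so it does not settle the variances either.

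A reader might also infer that the covariance can be picked freely once results are seen. That goes too far. The order is fixed in advance, and the protocol refers the details to the SAP. The only discretion is over when to step to the next structure. What remains is that the undefined condition governs that step, goes beyond the trigger the protocol names, and is not declared in Appendix 4.

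Finally, the consequence is small. The primary analysis is Barnard's exact test and is unaffected. Protocol Section 9 calls all results exploratory, no multiplicity adjustment is made, and SDs by visit will be tabulated, so unequal variances would be visible. The addendum reports that the study was terminated for lack of efficacy, so no positive decision rests on these contrasts. All of this stands and sets the severity.

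**Conclusion.** The point holds in a limited form. If the unstructured fit is abandoned, the SAP offers only equal-variance structures for a contrast at one visit. The Week 8 standard error for QMG and MG-ADL is then wrong whenever the Week 8 variance differs from the common variance fitted across visits. Against a nominal 10%, the error is about 13-20% for the linear rises examined, 12-13% for the 2.2 to 3.2 plateau, 10% for constant SD, and 7% and 4% for the two falling paths. These figures rest on assumed SDs and correlations and on complete data. With missing data the choice of covariance would also move the estimate itself, which was not quantified here.

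The undefined trigger is a separate defect that does not depend on which way the variance moves. Nothing in the documents shows that the fallback was used. Severity is minor.

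**What to change.** - **Order.** After unstructured, try TOEPH, ARH(1) and CSH, and only then TOEP, AR(1) and CS. Keep Kenward-Roger throughout.
- **Trigger.** Replace the poor-performance condition with objective computational criteria: non-convergence, or a covariance or Hessian matrix that is not positive definite. Simply deleting the condition would leave no rule for a fit that converges but cannot be used. Because this remains wider than the protocol's wording, record it in Appendix 4.
- **Reporting.** State in the CSR which structure was used for each endpoint and why. The Week 8 analysis has already been run, so this is the part that can still be applied in full. If an equal-variance form was used, show a heterogeneous fit beside it, labelled as added later.

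A sandwich standard error is not the better route here. It would have to be reconciled with the specified Kenward-Roger method, and it tends to be too small with about 14 participants in the 120 mg arm.

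The cost is SAP and CSR wording, plus up to 7 more variance parameters in the fallback model, still well below the 36 of the unstructured matrix. CSH can be slightly conservative, with a standard error about 6% too large if the true correlation is autoregressive; placing it last of the three limits that.

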5.4.1.8. Supplemental Analyses for the Secondary Endpoints

Supplemental analyses on select secondary endpoints (MMRM analysis as specified in Section 5.4.1.1, Section 5.4.1.2, and Section 5.4.1.3) will be performed based on the PPS in the same manner as done for the FAS. The purpose of these supplementary analyses is to provide additional insights for secondary efficacy results in a more compliant subgroup of the study population.

| Endpoint | Analysis | Population | Method | Missing Data/Intercurrent Event Handling |
|---|--------------------------|------------|---|---|
| Change from Baseline in the QMG total score at Week 8 | Primary Secondary | FAS FAS | MMRM Jonckheere-Terpstra trend test | No imputation will be implemented. Analyses will be performed regardless |
| | Primary supplementary | PPS | MMRM | |

Table 2:Summary of Secondary Endpoints

| Endpoint | Analysis | Population | Method | Missing Data/Intercurrent Event Handling |
|--|----------------------------|------------|--|--|
| | Secondary supplementary | PPS | Jonckheere-Terpstra trend test | of use of rescue therapy. |
| Change from Baseline | Primary | FAS | MMRM | For the responder endpoint (defined at various points of improvement) at a specific visit, only participants who have nonmissing |
| in the Neuro-QoL Fatigue total score at Week 8 | Secondary | FAS | Jonckheere-Terpstra trend test | |
| | Primary supplementary | PPS | MMRM | |
| | Secondary supplementary | PPS | Jonckheere-Terpstra trend test | assessment at the specific study visit |
| Change from Baseline in the MG-ADL total score at Week 8 | Primary | FAS | MMRM | will be included in the analysis for that particular visit. |
| | Secondary | FAS | Jonckheere-Terpstra trend test | |
| | Primary supplementary | PPS | MMRM | |
| | Secondary supplementary | PPS | Jonckheere-Terpstra trend test | - |
| Proportion of participants with at least a 3-, 4-, 5-, 6-, 7-, or 8-point improvement in the QMG total score at Week 8 | Primary | FAS | Exact 2-sided 90% CIs using the Clopper-Pearson method for proportions and 2-sided 90% CIs using the Chan and Zhang method (Chan, 1999) for difference in proportions | |

Table 2:Summary of Secondary Endpoints

| Endpoint | Analysis | Population | Method | Missing Data/Intercurrent Event Handling |
|--|----------|------------|--|--|
| Proportion of participants with at least a 2-, 3-, 4-, 5-, 6-, 7-, or 8-point improvement in the MG-ADL total score at Week 8 | Primary | FAS | Exact 2-sided 90% CIs using the Clopper-Pearson method for proportions and 2-sided 90% CIs using the Chan and Zhang method (Chan, 1999) for difference in proportions | |
| Proportion of participants with at least a 3-, 4-, 5-, 6-, 7-, or 8-point improvement in the QMG total score in any 4 consecutive weeks during the first 8 weeks and who did not receive rescue therapy | Primary | FAS | Exact 2-sided 90% CIs using the Clopper-Pearson method for proportions and 2-sided 90% CIs using the Chan and Zhang method (Chan, 1999) for difference in proportions | Participants who discontinued early without achieving the prespecified point improvement from the Baseline in any 4 consecutive weeks during the first |
| Proportion of participants with at least a 3-, 4-, 5-, 6-, 7-, or 8-point improvement in the MG-ADL total score in any 4 consecutive weeks during the first 8 weeks and who did not receive rescue therapy | Primary | FAS | Exact 2-sided 90% CIs using the Clopper-Pearson method for proportions and 2-sided 90% CIs using the Chan and Zhang method (Chan, 1999) for difference in proportions | 8 weeks will be considered as nonresponders. Participants who received rescue therapy anytime during the first 8 weeks will be considered as nonresponders. |

| Table 2: | Summary of Secondary Endpoints |
|----------|--------------------------------|
|----------|--------------------------------|

Abbreviations: CI = confidence interval; FAS = Full Analysis Set; MG-ADL = Myasthenia Gravis Activities of Daily Living; PPS = Per Protocol Set; QMG = Quantitative Myasthenia Gravis

5.5. Tertiary/Exploratory Endpoints Analyses

All exploratory endpoint analyses will be performed on the FAS population, unless specified otherwise. For Group 1 and 2 (PEP, ETP and OLE Period, if applicable), baseline is defined as the last available assessment prior to the first dose of ALXN2050. For Group 3 (the PEP of the placebo arm), baseline is defined as the last available assessment prior to the first dose of placebo. For Groups 3a and 3b (ETP and OLE Period, if applicable, of placebo arm), 2 baselines are defined: the PEP baseline is defined as the last available assessment prior to the first dose of placebo and the ETP baseline is defined as the last available assessment prior to the first dose of ALXN2050. No formal hypothesis testing is planned. Unless otherwise specified, no imputation will be implemented.

5.5.1. Tertiary/Exploratory Endpoints Analyses at Analysis 1 (Week 8)

This section describes all exploratory analyses to be performed at the first analysis when all participants have completed the first 8 weeks of treatment or have discontinued from treatment.

5.5.1.1. Dual Responder in MG-ADL and QMG

The FAS will be used for this analysis.

Responder is defined as participants with both an MG-ADL total score reduction of ≥ 2 points and a QMG total score reduction of ≥ 3 points in any 4 consecutive weeks during the first 8 weeks and who did not receive rescue therapy. The number and proportion of responders will be summarized by treatment group. The exact (Clopper-Pearson) 90% CI for each treatment group will be presented. The differences in proportions between each of the ALXN2050 dose groups (180 mg bid or 120 mg bid) and the placebo group will be presented, along with 2-sided 90% CIs using the Chan and Zhang method (Chan, 1999). The same intercurrent event handling approach will be followed as specified in the primary analysis of the primary endpoint in Table 1.

5.5.1.2. Proportion of Participants With 2-Point Improvement in the MG-ADL Total Score for 4 Consecutive Weeks and Who Did Not Use Rescue Therapy

The FAS will be used for this analysis.

This analysis includes MG-ADL data of the first 8 weeks (Groups 1, 2, and 3) and Week 8 to 16 data for Groups 3a and 3b participants who have completed Week 16 assessment or discontinued prior to Week 16 by the data cutoff date.

The proportion of participants with at least a 2-point improvement in the MG-ADL total score for 4 consecutive weeks (measured from Day 1 [PEP baseline] to Week 8 for Groups 1, 2, and 3 and from Week 8 [ETP baseline] to Week 16 for Groups 3a and 3b) and who did not receive any rescue therapy will be summarized. The exact (Clopper-Pearson) 90% CI for each group will be presented. Summaries using the PEP and ETP baselines will be both presented for Groups 3a and 3b. The same intercurrent event handling approach will be followed as specified in the primary analysis of the primary endpoint in Table 1.

For Groups 3a and 3b, this endpoint will be summarized in a shift table presenting the shift in responder status from the first 8 weeks to Weeks 8 to 16 (using the PEP and ETP baselines separately for Week 8 to 16 responder status). The observed frequencies and percentages, together with an exact (Clopper-Pearson) 90% CI for the true percentage of responders, will be presented for the first 8 weeks and Weeks 8 to 16 separately. The difference in percentages of responders (Weeks 8 to 16 [first 8 weeks]) and corresponding 90% CI for the true difference will also be presented for each group.

5.5.1.3. Change From Baseline in the MG-ADL Total Score at Week 8 for Groups 1, 2, and 3 and From Weeks 8 to 16 for Groups 3a and 3b

The FAS will be used for this analysis.

This analysis includes MG-ADL data of the first 8 weeks (Groups 1, 2, and 3) and Week 8 to 16 data (and beyond) for Group 3a and 3b participants by the data cutoff date.

Change from Baseline in the MG-ADL total score at Week 8 for Groups 1, 2, and 3 and change from the PEP and ETP baselines in the MG-ADL total score at Week 16 for Group 3a and 3b will be summarized in descriptive statistics. Change from Baseline in the MG-ADL total score by all study visits up to the data cutoff date and treatment group will be summarized in descriptive statistics.

Summaries using the PEP and ETP baselines will be presented separately for Group 3a and 3b.

5.5.1.4. Change From Baseline in the MG-ADL Total Score at Week 26 for Groups 1 and 2

This analysis will be covered in the analysis in Section 5.5.1.5.

5.5.1.5. Change From Baseline in the MG-ADL Total Score at Week 26 for Group 1 and 2 and From Weeks 8 to 34 for Groups 3a and 3b

This analysis includes MG-ADL data of the first 8 weeks (Group 1, 2, and 3) and Week 8 to 34 data for Group 1, 2, 3a, and 3b participants.

Change from Baseline in the MG-ADL total score at Week 26 for Groups 1 and 2 and change from Baseline in the MG-ADL total score at Week 34 for Group 3a and 3b will be summarized. Change from Baseline in the MG-ADL total score by all study visits up to the data cutoff date and treatment group will be summarized. Additional OLE Period data after Week 34 within the data cutoff date will be included, if applicable. Summaries using the PEP and ETP baselines will be both presented for Groups 3a and 3b.

Note that the output supporting this analysis will be covered in the output produced in Section 5.5.1.3.

